13.4 Combined Solicited and Unsolicited Adverse Events

A summary of subjects with all combined solicited (regardless of their duration) and unsolicited adverse events will be provided. Solicited adverse events will be coded by MedDRA. For clintrial.gov posting purposes, a summary of combined solicited and unsolicited non-serious adverse events will be produced by System Organ Class and according to occurrence of each event based on the Overall Safety set.

Pausing rules

Review of safety data will be conducted at an ongoing basis to check if the pre-defined pausing rules have been met. A summary table will be created with number and % of subjects who met one of the criteria by treatment based on the Overall Safety set.

- Any SAE that cannot be reasonably attributed to a cause other than vaccination, according to the Investigator's assessment, within 28 days post-vaccination (i.e. probable).
- Severe systemic hypersensitivity such as anaphylaxis, within 24 hours after study vaccination.
- Any Grade 3 (severe) local solicited AE lasting ≥2 consecutive days, within 7 days postvaccination.
- Any Grade 3 (severe) systemic solicited AE lasting ≥2 consecutive days, within 7 days postvaccination.
- Any severe unsolicited AE that cannot be reasonably attributed to a cause other than vaccination (i.e. probable), within 7 days postvaccination.

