## **3.8 Stopping/Pausing Guidelines**

aQIVc has never been administered to humans. Therefore, additional safety precautions have been included in this study. The IST, which is independent of the clinical study team involved in the execution of the study, will review the safety information at two timepoints during the study conduct, using pause rules as provided in [Table 3-1](#). Safety reviews by the IST will be performed as soon as a 7-day safety follow-up data are available for the first 40 and 120 enrolled subjects. In addition, ad-hoc safety reviews can be scheduled if needed. If a pause rule is met or any safety concern is identified by the IST, the enrolment into the study and study vaccination will be paused pending the independent Data Monitoring Committee (DMC) review. It is the Sponsor's responsibility to put the enrolment (or the study vaccination) on hold at all sites via the IRT. The DMC will review all available safety

data and make a recommendation to the Sponsor whether the study should be permanently stopped, modified or continue unchanged. The final decision will be made by the Sponsor in consultation with the DMC (and, if needed, the Investigators). The decision will be documented and provided in writing to the investigators.

Independent of the DMC, the Sponsor can halt the study at any time. If the study is halted, the Sponsor or delegate will promptly notify the health authorities and investigators, who will promptly inform the study subjects and local Ethics Committee/ Institutional Review Board (EC/IRB) as per local regulations. Study vaccinations and further enrolment will only occur after written authorization is provided by the Sponsor in conjunction with a recommendation to proceed by the DMC and in consultation with the health authorities and EC/IRB, as appropriate.

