**Table 3-1: Pause Rules for Planned IST Review**

No	Pause Rule Criteria	No. of subjects
1	Any SAE that cannot be reasonably attributed to a cause other than vaccination a , according to the Investigator's assessment, within 28 days post-vaccination.	≥1 subject
2	Severe systemic hypersensitivity such as anaphylaxis, within 24 hours after study vaccination.	≥1 subject
3	Any Grade 3 (severe) local solicited AE lasting ≥2 consecutive days, within 7 days postvaccination	≥25% (and ≥2 subjects) in aQIVc group
4	Any Grade 3 (severe) systemic solicited AE lasting ≥2 consecutive days, within 7 days postvaccination	≥25% (and ≥2 subjects) in aQIVc group
5	Any severe unsolicited AE that cannot be reasonably attributed to a cause other than vaccination a , within 7 days postvaccination	≥10% (and ≥2 subjects) in aQIVc group

Notes: a at least probably related. Abbreviations: AE = adverse event; aQIVc = MF59-adjuvanted Quadrivalent Subunit Inactivated Cell-derived Influenza Vaccine IST = internal safety team; No. = number; SAE = serious adverse event.

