7.5 Safety Set

Solicited Safety Set

All subjects in the All Exposed Set with any solicited adverse event data collected on the electronic diary, including temperature measurements or use of analgesics/antipyretics.

Unsolicited Safety Set

All subjects in the All Exposed Set with results of the unsolicited adverse event assessments recorded. A record of safety assessment performed at a specific time point, with confirmation of no AE, is considered as adverse event data hence subject is to be included.

Overall Safety Set

All subjects who are in the Solicited Safety Set or in the Unsolicited Safety Set.

Subjects will be analyzed as "treated" (i.e., according to the vaccine a subject received, rather than the vaccine to which the subject may have been randomized).

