- 6. Day of first onset of solicited adverse events
- 7. Ongoing adverse events at Day 7
- 8. Distribution of maximum temperature
- 9. Other use of analgesics/antipyretics.

For each of the time points or time intervals presented in the summaries, only subjects with at least one valid observation (i.e., any non-missing values) for the solicited adverse events in the interval of interest will be considered. Subjects without valid data will be removed from the denominator to prevent a downward bias (towards zero).

All tables are run by vaccine group, overall and by age subgroup.

Overall summary of subjects with solicited adverse events.

Any solicited adverse event presence is defined as at least one day recorded a presence of a local or a systemic adverse event. No solicited adverse event is defined as for all days 'No' for all predefined solicited adverse events.

Note that, where applicable, missing values for all days for all events will be excluded from % calculations.

The use of analgesics/antipyretics will be considered in this summary as a separate category under "other", however will be considered as part of reactogenicity.

16 MAR 2021 Final Version 2.0

Local Solicited adverse events, maximum event severity by event and time interval

The **maximum event severity** will be defined if there is at least one non-missing observation within this time interval. Each subject's data will be aggregated across the time points of the interval and summarized according to the maximal severity observed for each local adverse event, followed by a summary across subjects for each vaccine. Subjects with missing values at each of the requested time points, will be excluded.

The time intervals will be Day 1 to Day 7, Day 1 to Day 3 and Day 4 to Day 7. A summary table will be created with the frequency using only any local solicited AE and severe local solicited events.

Systemic adverse events, maximum event severity by event and interval

The analysis on the maximum severity of the systemic adverse events will be done along the same methods as for the local adverse events.

Number of days with solicited adverse events

The number of days with the adverse event is defined irrespective of severity. If a solicited adverse event continues beyond day 7 the period after day 7 is added.

The frequency distribution of the number of days (including mean and median values) will be provided in a summary table by vaccine and by adverse event.

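### The SAP's pause-rule table puts the two solicited Grade 3 criteria on the Overall Safety Set, against the plan's own denominator rules, so its percentages are biased towards zero when diaries are blank

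*SAP*

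**What the plan says.** Protocol Table 3-1 lists five pause criteria. Criteria 3 and 4 concern Grade 3 solicited local and systemic events lasting at least two consecutive days within 7 days of vaccination. Their threshold is "≥25% (and ≥2 subjects) in aQIVc group", and the table names no analysis set. Protocol 3.8 schedules the IST reviews for when "7-day safety follow-up data are available for the first 40 and 120 enrolled subjects".

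SAP 13.4 repeats the five criteria without their thresholds and plans one summary table giving the "number and % of subjects who met one of the criteria by treatment based on the Overall Safety set". SAP 7.5 defines that set as "All subjects who are in the Solicited Safety Set or in the Unsolicited Safety Set". Entry to the Solicited Safety Set requires "any solicited adverse event data collected on the electronic diary". Entry to the Unsolicited Safety Set requires only a recorded assessment; one "with confirmation of no AE, is considered as adverse event data hence subject is to be included".

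Three other places treat solicited events differently:

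- Protocol 8.4.3.1.5 assigns the Solicited Safety Set to solicited events and the Unsolicited Safety Set to unsolicited ones.
- SAP 13.2 bases its analyses on the Solicited Safety Set and adds: "Subjects without valid data will be removed from the denominator to prevent a downward bias (towards zero".
- SAP 8.2 treats a diary with nothing recorded over the 7 days as missing and leaves it out of the safety analysis. A diary with at least one completed day is used as it stands.

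**The concern.** Under Protocol 3.6.2 the eDiary is the sole permitted source for solicited events once the 30-minute observation ends. A vaccinated subject who never fills it in can still enter the Overall Safety Set through the Day 7 call or the Day 29 visit. In the SAP 13.4 table that subject is in the denominator of criteria 3 and 4 but cannot enter the numerator.

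The error has one direction: it can pull a percentage below 25% but never lift one above it. SAP 13.2 names this bias and guards against it for the reactogenicity tables. SAP 13.4 has no such guard, although its percentages correspond to a threshold in the protocol. The vaccine is first-in-human and the planned safety reviews involve small arms, so a reader who sets this table beside Table 3-1 could take a criterion as unmet because of blank diaries.

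**Working it through.** The 25% is a chosen threshold, not a derived figure, so there is no calculation in the plan to reproduce. The check is how the two denominators read against it.

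**Inputs**

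- Threshold: at least 25% and at least 2 subjects in the aQIVc group (Protocol Table 3-1).
- Review points: 40 and 120 enrolled subjects (Protocol 3.8).
- Allocation 1:1:1:1 (Protocol 3.1), so about 40/4 = 10 and 120/4 = 30 aQIVc subjects. These are expected sizes; actual arms will vary.
- Subjects with a wholly blank diary: not given. Assumed range 0 to 3 of 10 and 0 to 6 of 30. The 5% in SAP 8.2 only triggers extra tables and is not an expected rate.

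**Formulas.** Let N be the aQIVc subjects in the Overall Safety Set, m those with a blank diary, and e those meeting the criterion.

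- Planned reading: e/N. Reading among subjects with diary data: e/(N − m).
- Their ratio is (N − m)/N = 1 − m/N, so the planned reading is never the higher one, and the two agree when m = 0.
- Smallest count that reaches the threshold on a denominator n: max(2, 0.25n rounded up).

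**Configurations where the reading changes**

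| N | Blank (m) | Events (e) | Overall Safety Set | Subjects with diary data |
|---|---|---|---|---|
| 9 | 1 | 2 | 2/9 = 22.2% | 2/8 = 25.0% |
| 10 | 2 | 2 | 2/10 = 20.0% | 2/8 = 25.0% |
| 12 | 4 | 2 | 2/12 = 16.7% | 2/8 = 25.0% |
| 29 | 1 | 7 | 7/29 = 24.1% | 7/28 = 25.0% |
| 30 | 2 | 7 | 7/30 = 23.3% | 7/28 = 25.0% |
| 30 | 3 | 7 | 7/30 = 23.3% | 7/27 = 25.9% |
| 30 | 6 | 6 | 6/30 = 20.0% | 6/24 = 25.0% |
| 120 | 4 | 29 | 29/120 = 24.2% | 29/116 = 25.0% |

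**Counts needed to reach the threshold (Overall Safety Set versus subjects with diary data)**

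- N = 10: 3 versus 3 with one blank diary; 3 versus 2 with two or three.
- N = 30: 8 versus 8 with one blank; 8 versus 7 with two to five; 8 versus 6 with six.
- One blank diary is enough at sizes such as 9 or 29. At 12, 28 or 32 it takes four.

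**Probability that the table reads 25% or more.** Assume a true rate of 25% among subjects with diary data, with e binomial on N − m.

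- N = 10, m = 2: P(e ≥ 2 of 8) = 0.63 on the diary denominator; P(e ≥ 3 of 8) = 0.32 on the Overall Safety Set.
- N = 30, m = 2: P(e ≥ 7 of 28) = 0.57 versus P(e ≥ 8 of 28) = 0.40.
- N = 30, m = 3: P(e ≥ 7 of 27) = 0.53 versus P(e ≥ 8 of 27) = 0.36.

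**The case against.** The strongest reply is that no pause decision is shown to rest on this table. Protocol 3.9 and SAP 15 leave IST procedures to a charter that is not among the documents, and SAP 4.2 has unblinded teams prepare the IST reports. SAP 13.4 lists the criteria without thresholds and tabulates every arm, although the percentage thresholds apply to aQIVc only. It can be read as a descriptive report table; if produced only at the end, it would cover about 120 aQIVc subjects after enrolment has closed. This stands. A reader might infer that the IST could miss a met criterion during enrolment, but the documents do not support that, because they do not say which denominator the IST uses. Against it, SAP 13.4 introduces the table with ongoing review against the pause rules, and its denominator is the only one the documents state for them.

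Other replies stand in part:

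- SAP 13.4 is not alone in using a wider set. The completeness summaries in SAP 13.1.1 use the All Exposed Set, and the combined posting summary in SAP 13.4 uses the Overall Safety Set. If the pause table has a single row for meeting any criterion, a common set is natural there. The conflict is with the 13.2 reactogenicity analyses and does not extend to every solicited summary.
- The SAP does not say that a blank diary counts as no reaction; that is the effect of the denominator. SAP 8.2 could be read as removing such subjects from this table too, but then it contradicts the set that 13.4 names. Either way the text needs settling.
- A subject without a diary is not invisible. A reaction reported verbally at a visit goes on the adverse event page as unsolicited (Protocol 3.6.2), and a severe one could count under criterion 5 if judged at least probably related. It still cannot count under criteria 3 or 4.
- Blank diaries should be uncommon. One entry puts a subject in the Solicited Safety Set, and Protocol 5.3 and 5.3.1 provide reminders, non-compliance alerts and a call after two missed days. The table also shows counts, and the IST may act on any safety concern. These limit the size of the bias but do not justify the denominator.

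**Conclusion.** The denominator in SAP 13.4 conflicts with Protocol 8.4.3.1.5, SAP 13.2 and SAP 8.2. For the two solicited criteria it biases the tabulated percentage towards zero by the factor 1 − m/N whenever m of N diaries are wholly blank. That follows from the text and needs no assumption about rates.

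Whether the bias carries a reading across 25% depends on unstated quantities. At the expected arm sizes of 10 and 30 it takes at least two blank diaries and an event count just at the margin. It would be too strong to say that one missing diary is enough in general: that holds at sizes such as 9 or 29. With about 120 aQIVc subjects the distortion is small, and with no blank diaries there is none. The count part of the threshold (at least 2 subjects) is unaffected. The conclusion concerns the SAP table only and makes no claim about the IST's working denominator.

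**What to change.** Reconcile SAP 13.4 with Protocol 8.4.3.1.5, SAP 8.2 and SAP 13.2, and state the analysis set for each criterion:

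- Rows for the two solicited criteria: the Solicited Safety Set, with SAP 13.2's requirement of valid diary data.
- Rows for the serious adverse event, hypersensitivity and severe unsolicited criteria: the Overall Safety Set, as now.
- Add, by arm, the number of vaccinated subjects without diary data.
- Confirm that the IST charter uses the same denominators, or record why it differs.

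The choice of denominator affects how many events the table needs before it shows 25% (3 or 2 in the example of 10 subjects with 2 blank diaries). The sponsor should therefore confirm which denominator Table 3-1 was meant to carry. The thresholds and the pause decision stay with the sponsor.

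The cost is a sentence or two in the SAP, a changed denominator for two rows of one table, one added count and a check of the charter. No new data are needed.

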13.5 Clinical Safety Laboratory Investigations

Not applicable.

13.6 Concomitant Medication

Medications and vaccines taken prior or during the study are categorized as pre-trial and/or concomitant. In addition, a subset of concomitant medications is defined for the period Day 1 to 29 (see section 8.7 for definition).

Medications (generic drug name) will be coded using the WHODRUG dictionary.

The frequencies and percentages of subjects reporting pre-trial, concomitant medications (Day 1 -29 and Day 1 to end of study) will be tabulated by vaccine group.

16 MAR 2021 Final Version 2.0

14. INTERIM ANALYSIS

There are no planned interim analyses for this study.

The statistical analyses will be performed stepwise in two parts, as follows:

1. A final analysis including all immunogenicity and safety data collected from Visit 1 to Visit 3 (Day 29) and associated primary and secondary objectives will be conducted on cleaned and locked data. No individual listings and unblinding data will be generated at this stage. Access to information about study groups will be limited by a biostatistician in charge of statistical analysis.

2. The analysis of immunogenicity and safety data collected between Visit 3 and Visit 5 will be performed after all data is available. The results of this analysis will cover the entire study duration. All results will be presented in the clinical study report and will include individual data listings and unblinded information.

16 MAR 2021 Final Version 2.0

15. DATA MONITORING COMMITTEES

An internal safety team (IST) – independent of the study team - will be installed to monitor the safety data collected during the enrollment of the subjects in the study. Details are included in the IST charter. In addition, upon request an independent DMC will be asked to review the safety data and make recommendations for the conduct of the trial. Further details are described in the DMC charter.

16. CHANGES TO PLANNED ANALYSIS

Compared to the final protocol, one optional exploratory analysis has been added on the comparability of the cell-based and egg-based titers. Details will be described in a separate analysis plan. For the primary endpoints, the GMT and the % of subjects with HI >=1:40, Day 1 was added to assure that we include the pre-vaccination results.

The statistical analysis plan was amended before unblinding. The following changes since version 1.0 16 Jun 2020 were made:

Section	Change	Rationale
8.7	Unsolicited adverse events before	This was requested by the US
	vaccination will be mapped to medical	regulatory agency (FDA CBER).
	history	
11.2	Analysis of GMT ratio: Adjusted estimates	All subgroup analyses, including the
	of GMT ratio by age subgroup will be	age subgroup, will be conducted in a
	calculated using the same model excluding	similar way by subgroup.
	the factor age subgroup.	
11.2	Analysis of binary endpoints: Additional	Factor pre-vaccination titer was
	supportive analyses will be done using	removed from the model due
	generalized linear models without the factor	expected convergence issue leading
	for pre-vaccination titer.	to non-estimable treatment effects.
13.2	Clarification added that the temperature will	Needed for programming to apply
	be converted to °C in one decimal.	the grading for the temperature

17. LIST OF FINAL REPORT TABLES, LISTINGS AND FIGURES

The list of tables, listings and figures will be developed based on the final version 1.0 of this statistical analysis plan. This will be documented as part of the TLF shells.

Numbering will follow ICH E3 guideline on clinical study report.

